- a. Design: This equivalence study will use an experimental design with randomization of parents seeking behavioral treatment for their 2-5 year old children at the Family Center (FC) in [name]. Equivalence studies are used to determine whether a novel treatment or health delivery model, that might be less costly or more acceptable to the treatment population, is at least as effective as another more well-established treatment. It is important to note that the participants in this study, who experience multiple adversities associated with urban poverty and mental health problems, may require more therapeutic services than just PT. As a result, parents and children may receive additional treatment (e.g., individual therapy, medication) other than PT. However, PT treatment (PCIT or CPP) will be randomly assigned and all additional therapies provided to the participating parent or child at the Family Center or other agencies during the course of this study (type, amount, and cost) will be accounted for in the study and included as co-variates in the analyses. In addition, the effect of parent depression and stress on PT outcomes will be evaluated. The strengths of this design include (a) the ability to determine whether families exposed to one PT program need more additional treatment than families exposed to the other PT program, (b) the ability to estimate the costs of additional therapy, (c)

Date: _ January 30, 2012 _____
 Principal Investigator: _ [name] _____
 Application Number: _ NA_00039328 _____

greater buy-in from clinicians who may be concerned that randomization will negatively affect treatment outcomes for their families, and (d) enhanced external validity of the study.

This study will use a block randomization procedure to facilitate the initiation of parent groups without lengthy waiting periods. Each block will consist of the next 19 eligible parents (estimated recruitment time=3-4 months). Following intake assessment by a FC clinician to determine study eligibility, parents who meet the inclusion criteria will be invited to participate in the study. Parents who state interest in participating and agree to have their name given to the Project Director will meet individually with the Project Director (to be hired) who will describe the study and obtain informed consent. Documentation of parent's agreement to be contacted by the Project Director will be placed in the child's medical record.

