Parents randomized to PCIT will be scheduled for weekly individual sessions with the target child led by trained PCIT therapists. Each treatment session is 1 hour. Parents randomized to CPP will be randomized to a weekly parent group led by trained CPP therapists. Each CPP session is 2 hours, scheduled on week-day evenings. Target children do not participate in CPP groups; therefore, childcare will be provided at no charge to facilitate parent attendance. Though PCIT and CPP each prescribe approximately 24 hours of treatment exposure, PCIT occurs over a longer period of time (usually 6-8 months versus CPP which occurs over 3 months). This is because (1) PCIT sessions are 1 hour shorter, and (2) PCIT treatments are delayed when parents cancel or do not show up for appointments whereas CPP group sessions continue even if some parents do not attend. All CPP sessions will be audio recorded and a random selection of CPP sessions will be reviewed for fidelity by [name] at Rush University. A random number of PCIT sessions will be videotaped and reviewed for fidelity by a research colleague certified in PCIT who works at the University of Maryland, [name]. A data use agreement will be obtained between [name] and [name] and [name].

- c. Blinding: parents and therapists cannot be blinded to treatment condition. Research assistants trained to code video recorded parent-child free play and clean-up sessions will be blind to treatment condition and hypotheses.
- d. Participants will have full access to routine care at the Family Center. If a PCIT therapist determines at the beginning of the session that the parent is in crisis (e.g., reports severe depression, domestic violence), or the parent requests using the session to discuss a non-child related crisis, they may decide to use that session for crisis intervention. This session will be documented as a non-PT session and accounted for in the analysis of total PT and non-PT treatment exposure. If the CPP therapist determines that a parent in the parent group is in crisis, or a parent requests to discuss a non-child related crisis, that therapist will meet with the parent after the CPP group to discuss scheduling a separate session.
- e. There is no control or placebo group. Participants in both conditions receive an evidence-based parenting program delivered by trained therapists.

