Exclusion criteria are parent(s) who (a) has (have) severe mental illness that would interfere with their ability to participate in PT (measured by the Psychosis Subscale of the Basic-24 or diagnostic intake clinician assessment) and/or (b) is (are) actively using drugs or alcohol, based on clinician assessment at intake. Foster parents or relatives without legal status for the child are excluded since they may not be able to complete the study.. Children who are actively suicidal, psychotic, or who have significant developmental delay (i.e., fail developmental screening using Ages and Stages Questionnaire at intake), congenital, genetic, or sensory abnormalities that interfere with the child’s understanding, cooperation, and/or participation in PCIT or CPP will be excluded and referred for appropriate treatment services or hospitalization. Children diagnosed with autism or Pervasive Developmental Disorder will also be excluded since there is no evidence that CPP or PCIT is effective with these populations.

6. Drugs/ Substances/ Devices

- a. NA
- b. NA.
- c. NA

7. Study Statistics

- a. Primary outcome variables: Child behavior problems (parent report and observed from video recorded parent-child play/clean-up), parenting self-efficacy, parent discipline, parent behavior (observed from video recorded play/clean-up), parent satisfaction, parent engagement in the intervention, parent attendance in PT sessions.
- b. Secondary outcome variables: cost variables are those related to (1) time required to administer PT (including lost time for missed appointments) and additional non-PT therapy services used by parent or child (i.e., individual therapy, medications); (2) therapist time, (3) parent time, (4) childcare provided during CPP sessions; (5) space (including one-way mirror).
- c. Sample Size and Statistical Plan: Sample size in this equivalence study is designed to determine whether CPP is as effective as PCIT for the targeted clinical population (i.e., outcomes do not differ clinically or statistically). We used CBCL scores (child behavior problems) to estimate the sample size positing the null hypothesis that the absolute difference in the post intervention means between the CPP and PCIT groups will be > 0.5 standard deviations (i.e., > 5 point difference on the CBCL). The alternative hypothesis is that the absolute difference in the two means is less than or equal to 0.5

Date: January 30, 2012
Principal Investigator: [name]

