Application Number: NA_00039328

standard deviations. We will use the more conservative two-sided test. Thus, with 300 participants (150/condition) we will have 99% power to detect this difference using a two-sample comparison of means with alpha=0.05.

Hypothesis testing will mainly be conducted using repeated-measures MANOVA. Should the MANOVA be significant, univariate ANOVA will follow to identify the source of those differences. MANOVA was determined to be a more desirable approach than random regression models because MANOVA corrects for multiple tests of hypotheses. All baseline difference analyses and hypothesis testing will be conducted using 2-tailed tests and alpha =.05 (except tests to examine baseline differences between conditions, which will use .01 to correct for the multiple tests of hypotheses).

d. Early stoppage rules. Interventions will be discontinued if (a) more than 50% of parent participants in either condition report dissatisfaction on consumer satisfaction surveys with their assigned intervention or (b) more than 50% of child participants' CBCL scores (in either condition) worsen from baseline by $> .5$ SD. In this event, the research team will immediately convene with the members of the DSM committee to carefully review the protocol, reasons for dissatisfaction, and recommendations for change. A data safety and monitoring committee will meet early in the first year of the study to make additional recommendations for stoppage rules.

8. Risks

- a. Medical risks. Parent-Child Interaction Therapy and the Chicago Parent Program are psychosocial parent training interventions that have shown no evidence of medical risk. The major risks of this study are disclosure of confidential information and discomfort with the personal nature of some of the survey questions. These risks are no greater than what parents would be exposed to in a mental health treatment setting.
- b. Efforts to minimize risk. Efforts have been taken to minimize risk through appropriate training of research and clinical staff and the use of random number subject identifiers. All therapists have licensed and experienced therapists and have completed the appropriate training (PCIT or CPP).

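### Adjusting for additional therapies received after randomisation means the CPP–PCIT contrast need not estimate the effect of assignment, and can bias the equivalence conclusion in either direction

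*Combined protocol and SAP*

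**What the plan says.** Section 4a (Design) allows families to receive treatment beyond the assigned parent-training (PT) program. Of the additional therapies "provided to the participating parent or child at the Family Center or other agencies during the course of this study", it says their "type, amount, and cost) will be accounted for in the study and included as co-variates in the analyses". It then lists among the strengths of the design "the ability to determine whether families exposed to one PT program need more additional treatment than families exposed to the other PT program".

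Section 4d describes how a crisis is handled in each arm. In PCIT the scheduled hour may be given over to the crisis: "This session will be documented as a non-PT session and accounted for in the analysis of total PT and non-PT treatment exposure". In CPP the group session goes ahead and "that therapist will meet with the parent after the CPP group to discuss scheduling a separate session".

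Section 7b includes "additional non-PT therapy services used by parent or child" in the secondary cost variables.

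Section 7c gives the analysis method: "Hypothesis testing will mainly be conducted using repeated-measures MANOVA". It names no covariates, does not say which models carry the section 4a adjustment, and does not specify an as-randomised comparison that leaves the additional therapies out. The only mention of intent-to-treat, in section 3, describes an earlier CPP trial.

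**The concern.** Randomisation makes the arms comparable at assignment. A covariate fixed before assignment preserves that comparability; one that assignment can change need not. By the protocol's own account, additional therapy may be of the second kind. Its use by arm is a question the trial sets out to answer, and it is part of an outcome.

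Section 4d shows one route by which recorded non-PT treatment could differ by arm even if need did not. A PCIT crisis turns an already scheduled hour into non-PT time, whereas a CPP crisis counts only if a separate session is arranged. Section 4b adds that PCIT usually runs 6–8 months and CPP 3 months.

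At stake is the main conclusion, that the two programs differ by no more than 0.5 SD. Suppose families who do poorly are given more additional therapy. Adjustment then removes part of a real gap and favours equivalence. Suppose instead that therapy helps and goes more to the less effective arm. Adjustment then widens the gap, and equivalence can be missed. No design feature determines which case applies.

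**Working it through.** **Inputs from the documents.** 150 per arm, margin 0.5 SD (5 CBCL points, so SD = 10), alpha 0.05, stated power 99% (section 7c).

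**The plan's own figure.** In SD units the standard error (SE) of the difference is √(2/150) = 0.1155. Two-sided power to detect 0.5 SD is Φ(0.5/0.1155 − 1.96) = Φ(2.37) = 0.991, so the stated 99% is reproduced. Two one-sided tests (TOST) at 5% with a true gap of 0 give 2Φ(4.330 − 1.645) − 1 = 0.993. Neither figure involves the covariates.

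**Assumptions not in the documents.** A single post-intervention comparison; outcome and therapy each with within-arm SD 1; a higher score is worse; CPP is the worse arm when the gap is positive. Equivalence is declared when the 90% interval lies inside ±0.5. TOST is assumed for illustration, since section 7c names MANOVA. All slopes and arm differences below are assumed.

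**Formulas.** Let b be the within-arm slope of outcome on therapy and dM the CPP-minus-PCIT difference in mean therapy.

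- Adjusted gap = unadjusted gap − b × dM
- SE = √[(1 − b²)(2/150 + dM²/298)]
- P(equivalence) = Φ((0.5 − 1.645·SE − gap)/SE) − Φ((−0.5 + 1.645·SE − gap)/SE), using the adjusted gap

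**Worked case.** Therapy only marks poor response, with correlation r. Then b = r and dM = r × gap. With r = 0.5 and a true gap of 0.50, dM = 0.25. The adjusted gap is 0.50 − 0.5 × 0.25 = 0.375 and SE = √[0.75 × (0.01333 + 0.00021)] = 0.1008. P(equivalence) ≈ Φ(−0.405) = 34%.

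| Scenario | True gap | b | dM | Adjusted gap | P(equivalence), unadjusted → adjusted |
|---|---|---|---|---|---|
| Marks poor response, r = 0.3 | 0.50 | 0.3 | 0.15 | 0.455 | 5% → 11% |
| Marks poor response, r = 0.5 | 0.50 | 0.5 | 0.25 | 0.375 | 5% → 34% |
| Helps; worse arm gets more | 0.50 | −0.3 | 0.25 | 0.575 | 5% → 1.0% |
| Helps; worse arm gets more | 0.50 | −0.3 | 0.50 | 0.650 | 5% → 0.15% |
| Helps; CPP gets more | 0 | −0.3 | 0.50 | 0.150 | 99% → 92% |
| Differs only by delivery or recording, CPP more | 0.50 | 0.3 | 0.25 | 0.425 | 5% → 17% |
| Differs only by delivery or recording, PCIT more | 0.50 | 0.3 | −0.25 | 0.575 | 5% → 1.0% |
| No difference by arm | 0.50 | 0.3 | 0 | 0.500 | 5% → 5% |

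In the two delivery-or-recording rows, b is positive because families in greater need receive more therapy. Simulation with 4,000 replicates per scenario agreed with these figures to within about one percentage point.

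**Second check, with an unmeasured level of need driving both therapy and outcome** (simulated, true gap 0.50). The mean adjusted estimate was 0.40 where confounding by need dominated (equivalence declared 22% of the time). It was 0.66 where helpful therapy went more to CPP (0.2%) and 0.34 where it went more to PCIT (41%). The unadjusted estimate was 0.50, with equivalence declared about 5% of the time, in all three.

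**The case against.** The strongest reply is that section 7c is the statistical plan and contains no covariates. It names MANOVA and ANOVA, and powers the trial on a two-sample comparison of means. On that reading the primary analysis is already unadjusted, and section 4a is design narrative. The crisis-session sentence in section 4d may likewise refer only to a separate exposure analysis. It is true that the plan does not say which models carry the adjustment. But section 4a states a rule for the analyses without restriction, and silence in section 7c neither limits nor overrides it. An analyst following section 4a would adjust.

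A second reply is that calling the shift a bias presumes the effect of assignment is the target, while the sponsor may want program effects net of co-treatment. The protocol states no such estimand, and simple adjustment would not in general deliver it. In the confounding-by-need simulation therapy had a direct effect of −0.1 and CPP received 0.5 SD more. The effect net of therapy was therefore 0.50 − (0.5 × −0.1) = 0.55. The adjusted estimate was 0.40, which matches neither target.

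A third reply is that the slopes are invented, the upper case needs a correlation of 0.5, and baseline is left out of the model, so the real slope could be smaller. This stands as a limit on size: the figures illustrate direction and sensitivity and are not error rates of the planned MANOVA.

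Finally, the documents do not expressly place the T1 assessment before assignment, and section 4b describes the block differently from section 4a. Both points affect the choice of adjusters but not the case for dropping the therapy covariates.

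**Conclusion.** The concern holds. The plan adjusts for variables that arise after randomisation and that it treats elsewhere as possibly differing by arm, so the adjusted contrast need not estimate the effect of assignment. The bias equals −b × dM and can favour or hinder an equivalence finding. It is zero in the linear model if therapy does not differ by arm.

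Under the assumed slopes and arm differences, a gap at the 0.5 SD margin appears as anything from 0.375 to 0.65 SD, or 3.75 to 6.5 CBCL points. The documents give no values from which the actual size could be predicted. The sample size and stated power are unaffected. This should be fixed: it bears on the trial's main conclusion and costs little to correct.

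**What to change.** 1. In section 7c, state that the primary effectiveness comparisons (objectives 1 and 2, and any other between-arm outcome model that would carry these covariates) compare arms as randomised, without additional-therapy covariates. Limit adjustment to variables fixed before assignment: the T1 value of the outcome, once it is confirmed that T1 precedes assignment, and the randomisation block as defined in section 4a (successive sets of 19 eligible parents). The section 4b description, by next CPP group or PCIT therapist, should not be used for this because it separates by arm.
2. In section 4a, replace the covariate commitment with a statement that additional therapy is compared by arm as an outcome and used in the cost-consequence analysis under objective 4, both already planned.
3. Label any therapy-adjusted model as sensitivity or exploratory, and state what it is meant to estimate and under what assumptions.

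The cost is about one sentence in each of sections 4a and 7c. No new data are needed, sample size and care do not change, and the therapy data remain in use.

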Using a randomized experimental design, 300 parents of 2-5 year old children (predominantly African American and economically disadvantaged) referred for behavior problems to the Family Center at Kennedy-Krieger Institute will be randomized to Parent-Child Interaction Therapy (PCIT; n=150) or Chicago Parent Program (CPP; n=150). Data on child behavior problems, parent discipline strategies, parenting self-efficacy, observed parent behavior, parent stress, and depression will be obtained from all participants at baseline and post-intervention assessments. Social risk will be assessed at intake. Parent satisfaction, attendance, and engagement in the intervention will be obtained at post-intervention. Clinical costs related to PT and non-PT treatment will be measured monthly. This innovative study will be the first to compare the effectiveness, cost, and social validity of a brief treatment designed with and for ethnic minority parents of young children against a well-established treatment considered to be the "gold standard." Determining whether a PT treatment can yield comparable effects for low-income, racial/ethnic minority parents of young children but at less cost, in less time, and with greater social validity is of significant public health importance.

2. Objectives: To compare the:

1. Effectiveness of PCIT and CPP for reducing behavior problems in a predominantly African American sample of children 2-5 years old from low-income communities. It is hypothesized that CPP will be equally as effective as PCIT for reducing child behavior problems based on parent report and observation.
2. Effectiveness of PCIT and CPP for improving parenting behavior and self-efficacy among a predominantly African American sample of parents of 2-5 year old children from low-income communities. It is hypothesized that CPP will be equally as effective as PCIT for improving parent discipline, self-efficacy, and observed parenting behavior.
3. Perceived social validity of PCIT and CPP based on parent satisfaction scores, treatment attendance, and parent engagement ratings (i.e., active parent participation in the intervention

Date: January 30, 2012
Principal Investigator: [name]
Application Number: NA_00039328

sessions). It is hypothesized that parents in the CPP condition will (a) attend a higher percent of PT sessions, (b) be more engaged, and (c) report higher satisfaction than parents in PCIT.

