CPP groups are led by two trained group leaders using a standardized manual that lists specific discussion questions associated with each video vignette. Typically, 8-12 parents are enrolled in a 12-session CPP group (unlike PCIT, parents are encouraged to bring other family members to the CPP

Date: _ January 30, 2012 _____
Principal Investigator: _ [name] _____
Application Number: _ NA_00039328 _____

sessions for support). The vignettes are designed to stimulate discussion and problem-solving around each of the vignettes and the group leaders help parents tailor strategies to meet their childrearing goals. Although CPP group leaders are experts about the child behavior management strategies and program principles, they are trained to view parents as the experts about their own children. Thus, the parent groups are designed to help parents (a) clarify their childrearing goals and (b) select those strategies they believe will be most effective and most likely to advance their childrearing goals. This aspect of CPP lies in contrast to PCIT, where treatment progress is dependent on parents mastering each skill taught in the program before acquiring a new skill.

The CPP was rigorously evaluated in a randomized trial of 253 parents of 2-4 year old children in 7 childcare centers serving low-income families in Chicago (59% African American, 33% Latino). Parents in the CPP condition used less corporal punishment and had more positive observed interactions with their children at 1-year post-intervention when compared to control parents. In addition, their children exhibited significantly fewer behavior problems during observed parent-child interactions. Parents who attended at least half of the CPP sessions also reported higher parenting self-efficacy, more consistency in their discipline, and fewer behavior problems at home. In addition, teacher-ratings of children's behavior problems in child care showed significant improvements. Parent stress and depression did not moderate these outcomes. Moreover, consumer satisfaction was high; parents reported that they would highly recommend (85%) or recommend (15%) the program to other parents.

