b. Study duration and visits: Following consent, parents will be assigned to the appropriate block consisting of the next CPP group or the next available PCIT therapist. Participating parents and children will complete three assessment phases: baseline, 4 months post-baseline, and 9 months post-baseline. Each assessment phase includes parent-report surveys on child behavior problems, parenting self-efficacy, parent discipline strategies, stress, depressive symptoms, and attachment, and a 15- minute videotaped parent-child free play interaction (Dyadic Parent-Child Interaction Coding Systems; DPICS), followed by a clean-up session. Videotaped DPICS assessments will be coded by research colleagues at the University of Iowa ([name].) A Data Use Agreement will be obtained between Drs. [name], University of Iowa and [name], Johns Hopkins School of Nursing. Assessments typically require 45-75 minutes at each phase. All measures are described in Table 1 below.

Table 1. Parent-Child Variables, Measures, Informant, Items, Assessment Time-points*, Reliability, Validity

Variables	Measure(s)	Informant	# of Items	When Assessed	Reliability	Validity Evidence
Child Behavior Problems (parent)	Child Behavior Checklist (CBCL/1½-5) (Externalizing Scale & Internalizing Scale)	Parent	99	T1, T2, T3	.86-.89	[40; 41]
Child Behavior Problems (observed)	Dyadic Parent-Child Interaction Coding System (DPICS) (non-compliance, destructives, physical negatives, smart talk, cry, whine, yell)	Observer	7	T1, T2, T3	.73	[22; 57; 58]
Parent Self-Efficacy	Toddler Care Questionnaire (TCQ)	Parent	38	T1, T2, T3	>.93	[22; 57; 59; 60]
Parent Discipline	Parenting Questionnaire (PQ) (Warmth, Following Through, Corporal Punishment subscales)	Parent	50	T1, T2, T3	.68-.84	[22; 61]
Parent Depression	Center for Epidemiologic Studies Depression Scale-Revised	Parent	20	T1, T2, T3	>.85	
Parent Attachment	Attachment Style Questionnaire	Parent	40	T1	Test-retest .75-.80	
Parent Behavior	DPICS (Praise, Commands, Physical Coerciveness, Critical Statements, Positive/ Negative Affect)	Observer	10	T1, T2, T3	.88-.90	[22; 57; 58]
Social Validity: parent satisfaction w/ PT	Parent Satisfaction at end of program	Parent	4-12	T2 -CPP T3-PCIT	NA (items analyzed separately)	[34; 55; 57]
Social Validity: Degree to which parent actively participated in PT	Parent Engagement Scale	Clinician	7	T2-CPP T3-PCIT	.87	[35]

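### Parents are randomised in sequential accrual blocks, but the planned analysis has no term for block; adding one is a free, small gain in precision

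*Combined protocol and SAP*

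**What the plan says.** Section 4a (Design) sets out restricted randomisation with a practical aim: "This study will use a block randomization procedure to facilitate the initiation of parent groups without lengthy waiting periods". It then gives the size and pace of a block: "Each block will consist of the next 19 eligible parents (estimated recruitment time=3-4 months". Section 4b (Study duration and visits) adds that after consent "parents will be assigned to the appropriate block consisting of the next CPP group or the next available PCIT therapist".

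The Abstract states the planned allocation: families "will be randomized to Parent-Child Interaction Therapy (PCIT; n=150) or Chicago Parent Program (CPP; n=150". Section 7c (Sample Size and Statistical Plan) repeats it, "with 300 participants (150/condition", and derives 99% power for a 0.5 SD difference from a comparison of two means at alpha 0.05. Hypotheses are to be tested mainly by repeated-measures MANOVA, followed by univariate ANOVA. The only adjustment variables named, in section 4a, are therapies received in addition to parent training. Randomisation block, cohort, CPP group and therapist are not mentioned in the analysis.

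**The concern.** When allocation is restricted within blocks, the two programs are compared among families recruited in the same period. Differences between periods then largely cancel out of the comparison of programs. A model without block still counts those differences as noise. The estimated standard error is then a little larger than the design warrants, and the confidence interval a little wider.

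This matters in an equivalence trial because the conclusion depends on how the interval sits against the margin, here 0.5 SD or 5 CBCL points. Recruitment is also slow enough for the case mix, season or staffing to drift. What is at stake is a small amount of precision. The treatment estimate is not materially biased, and the false-positive rate is not raised by leaving out a block term that is common to both arms.

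**Working it through.** **Inputs.** Block size 19, at 3-4 months per block (section 4a). Total 300, 150 per arm (Abstract, section 7c). Margin 0.5 SD = 5 CBCL points, so the implied SD is 10 (section 7c). The share of outcome variance due to blocks is not in the documents; 2% and 5% are assumed.

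**1. The plan's own power figure.** In SD units, SE = √(1/150 + 1/150) = 0.1155. Power = Φ(0.5/0.1155 − 1.960) = Φ(4.330 − 1.960) = Φ(2.370) = 99.1%. The stated 99% reproduces. Read as two one-sided tests with a true difference of zero, power is 99.3% at 0.05 per side and 98.2% at 0.025 per side.

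**2. Number of blocks and duration.** 300/19 = 15.79, so 15 full blocks (285 parents) and 15 parents of a 16th. At the stated pace this takes 15.79 × 3 = 47 months to 15.79 × 4 = 63 months.

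**3. Gain from modelling block.** If blocks explain a share R of the variance, the error variance falls to (1 − R) of its value and the SE to √(1 − R).

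| Assumed R | √(1 − R) | SE, CBCL points | 1.96 × SE | Two-sample power |
|---|---|---|---|---|
| 0 | 1.000 | 1.155 | 2.26 | 99.1% |
| 2% | 0.990 | 1.143 | 2.24 | Φ(4.330/0.990 − 1.960) = 99.2% |
| 5% | 0.975 | 1.125 | 2.21 | Φ(4.330/0.975 − 1.960) = 99.3% |

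The SE falls by 1.0% to 2.5%. The 95% half-width falls by about 0.02 to 0.06 CBCL points.

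**4. Cost.** A fixed factor with 16 levels uses 15 degrees of freedom: 300 − 2 = 298 becomes 283. Using t ≈ 1.96 + (1.96³ + 1.96)/(4 × df), the critical value is 1.968 at both. A random block effect costs one variance parameter. Because 19 is odd, a block splits at best 10:9, which carries 10 × 9/19 = 4.74 units of information against 19/4 = 4.75 for an equal split. The loss is 0.3% in variance at most, below the assumed gain.

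**5. Does allocation matter here?** The split within a block is not stated, so three cases were checked.
- Constant 10 CPP : 9 PCIT: 150/135 after 15 blocks, 156-160 CPP at 300, and 160/144 after 16 blocks.
- Alternating 10:9 and 9:10: 143/142 after 15 blocks; a 7/8 split of the last 15 parents then gives exactly 150/150.
- Extra place assigned at random in each block (200,000 simulated trials): exactly 150/150 in about 18%, and a CPP arm of 147-153 in about 90%.

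Two-sample power is 99.1% at 158/142, 99.2% at 160/144 and 98.8% at 150/135. The largest change from 150/150 is about 0.3 points.

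**The case against.** The strongest reply is that nothing in the trial turns on this. Power is already 99%, the share of variance due to blocks is assumed, and omitting block is, if anything, conservative. All of that stands. It shows that the gain is small, not that it is absent, and it gives no reason to leave out a factor that the design itself creates.

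A second reply is that the block is a scheduling device. Section 4a gives a logistical purpose and counts eligible parents, who are invited and consented only afterwards, so fewer than 19 may be randomised from a block. Section 4b describes the block as the next CPP group or PCIT therapist, which is specific to one arm. This also stands in part. The point rests on the section 4a reading, in which each accrual block is divided between the two programs, and the number of blocks exceeds 16 if parents decline. The variable needs one definition before it can enter a model.

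A reader might go further and infer, from 19 being odd and not dividing 300, that 150/150 cannot arise and that the procedure does not produce the stated sample. The documents do not support that. They leave the split open, some splits give exactly 150/150, and recruitment can stop partway through a block. The figure of 150 per arm also reads naturally as a planning target. Nor does the accrual estimate conflict with anything, since no recruitment period is stated.

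**Conclusion.** The point holds as a minor improvement. The trial randomises within sequential blocks, about 16 for 300 parents, and the written analysis contains no block term. Under the assumption that blocks explain 2-5% of outcome variance, modelling block lowers standard errors by about 1-2.5% for about 15 degrees of freedom. If blocks explain nothing, the loss is negligible.

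This is not an arithmetic error in the plan: the stated power reproduces, and imbalance from blocks of 19 changes it by at most about 0.3 points. A reader might also infer that a block term settles the correlation among parents treated in the same CPP group ("Typically, 8-12 parents are enrolled in a 12-session CPP group"). It does not. That correlation exists in one arm only, whereas a block effect common to both arms describes the recruitment period. Group clustering is a separate issue and needs its own treatment.

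**What to change.** In section 7c, state that randomisation block enters every outcome model comparing CPP with PCIT, as a fixed or random factor chosen in advance. In the repeated-measures analysis it should be a between-family factor that also applies to change over time, so that it acts on the contrasts being tested. Record the block identifier for each family at randomisation.

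Reconcile sections 4a and 4b so that a block has one meaning, and say whether it counts eligible or randomised parents, how places are split within it, and what happens to an incomplete last block.

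The cost is one model term, about 15 degrees of freedom if fixed, and a few sentences of text, with no change to recruitment or sample size. Blocks of 20 split 10:10 (15 × 20 = 300, with 10 parents per CPP group, inside the typical 8-12) would be tidier, but that is optional and not a correction.
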